XEN45 Glaucoma Treatment System (referred to as XEN), comprised of the XEN Gel Implant (also referred to as the Gel Implant) and the XEN Injector (also referred to as the Injector) potentially alleviates this unmet need. Approximately 6 mm long and as wide as a human hair, this soft gelatinous stent is implanted via an *ab interno* surgical approach through a small, self-sealing corneal incision, to facilitate aqueous humor drainage from the anterior chamber to the subconjunctival space. The gelatin imparts hydrophilic properties that allow the Gel Implant to conform to the ocular tissue by expanding when hydrated upon contact with the aqueous humor. This expansion might minimize issues such as migration, erosion, and corneal endothelial damage observed in stents with synthetic materials.

The *ab interno* surgical approach for XEN is less invasive than traditional glaucoma surgeries and has several other advantages, including minimal trauma to the conjunctiva, maintenance of the natural drainage pathways, reduced scarring response, and the ability to accurately place the device under direct visualization of anatomy. Minimizing damage to the conjunctiva allows the possibility of future glaucoma surgery.

XEN is cleared in the United States for the management of refractory glaucomas, including cases when previous surgical treatment has failed, cases of primary open angle glaucoma (POAG), and pseudoexfoliative or pigmentary glaucoma with open angles that are unresponsive to maximum tolerated medical therapy. XEN is approved in multiple countries worldwide to reduce IOP in patients with POAG when previous medical treatments have failed.

XEN was prospectively studied in the United States in a multicenter, single-arm, open-label, clinical trial to evaluate its safety and effectiveness (XEN P13-001 Clinical Study Report; [Grover 2017](#)). This 12-month study was conducted in patients with refractory glaucoma when previous filtering or cilioablative procedures failed, or by experience was known to not provide satisfactory results, or IOP was unresponsive to maximally tolerated medication. Of the 65 subjects implanted (intent-to-treat population), at baseline, 85% of subjects had failed prior glaucoma procedures, 85% were using ≥ 3 hypotensives, and mean medicated IOP (SD) was 25.1 (3.7) mm Hg. At Month 12, 76% of subjects achieved $\geq 20\%$ IOP reduction from

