6.5 Withdrawal Criteria

Patients may voluntarily withdraw from the study at any time.

Patients who have their devices removed or have a suture placed to close the scleral channel, will be withdrawn from the study.

Patients who are not implanted with XEN during surgery will be withdrawn from the study and considered a screen failure. Investigators are recommended to follow the patient until they are stable.

The investigator will consider withdrawing a patient from the study early if any of the following criteria are met:

- Patient develops (or has an exacerbation of) a medical condition that, in the opinion of the investigator, compromises the patient's ability to participate in the study
- Patient is unwilling or unable to continue to comply with study procedures
- Patient is unwilling or unable to continue in the study

Whenever possible, the decision to withdraw a patient from the study or study treatment will be discussed with the sponsor.

7. Response Measures and Summary of Data Collection Methods

Detailed information on equipment and methodology to be used is provided in the Protocol Procedure Manual.

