## **7.0            PATIENT DISPOSITION**

Number and percent of patients who entered and completed the screening phase and who failed during the screening phase further broken down by most important failed criterion collected on the screening disposition electronic case report form (eCRF) and timing of failure collected on the subject qualification eCRF will be tabulated for all screened patients. Failed criteria include ‘Screen Failure’, ‘Adverse Event’, ‘Withdrawal by subject’, ‘Lost to Follow-Up’, ‘Pregnancy’, ‘Death’, ‘Physician decision’, ‘Protocol Deviation’, ‘Study Terminated by the Sponsor’, ‘Site Terminated by the Sponsor’ and ‘Other’. Under ‘Screen Failure’, timing of failure and inclusion/exclusion criterion not met will be presented.

Disposition summary tables for patients in the Implanted Population will be presented for study and study treatment. These tables will summarize the number and percent of patients who completed the study/study treatment and discontinued pre-maturely from study/study treatment further broken down by most appropriate reason for discontinuation as collected on the follow-up disposition and device complaint eCRF. Reasons for pre-mature discontinuation from the study include ‘Adverse Event’, ‘Withdrawal by subject’, ‘Lost to Follow-Up’, ‘Pregnancy’, ‘Death’, ‘Physician decision’, ‘Protocol Deviation’, ‘Study Terminated by the Sponsor’, ‘Site Terminated by the Sponsor’, ‘Technical Problems’, and ‘Other’. Reasons for pre-mature discontinuation from the study treatment include ‘Persistent hypotony that cannot be mitigated by other means’, ‘Uveitis, glaucoma and hyphema syndrome’, ‘Gross device malposition’, ‘Surgical procedure that requires explant (eg, trabeculectomy)’, and ‘Other’.

Study exit status will also be listed for all screened patients.

In addition, enrollment by region (Asia-Pacific, other) and study site will also be summarized in the Implanted Population.

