## **8.0 DEMOGRAPHICS AND OTHER BASELINE DATA**

### **8.1 DEMOGRAPHICS**

Following demographic characteristics will be descriptively summarized for the patients in the Implanted Population.

- Age (years)
- Age group (<60, 60-<70, 70-<80, ≥ 80 years)
- Sex (Male, Female)
- Race (White, Black or African American, Asian, American Indian or Alaska Native, Native Hawaiian or Native Pacific Islander, Multiple)
- Ethnicity (Hispanic or Latino, Not Hispanic or Latino)

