The variable ‘resp’ denotes the derived response variable as described above; ‘visit’ denotes the analysis visit month with the value 0 representing baseline; ‘pid’ is the unique patient ID; ‘bliop’ is the baseline Hour 0 IOP. Required proportion and 95% CIs at each assessment visit will be obtained by respectively applying the inverse logit transformation,  $\exp(\cdot)/(1+\exp(\cdot))$ , to ‘estimate’, ‘lower’ and ‘upper’ values contained in output dataset ‘lsms’ created by the ‘ods output’ statement. The proportion estimates and 95% CIs for Month 1, 3, 6, 8, 10 and 12 will be tabulated. In fitting the above model, missing data will not be imputed.

For Baseline and Month 12/Exit visits, Hour 0 IOP data from Hour 0 IOP eCRF page will be used. For all other visits without diurnal IOP assessment, all IOP collected for efficacy will be used.

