### 10.1.2 Sensitivity Analyses

A sensitivity analysis will be performed using descriptive summary statistics for the primary effectiveness endpoint but based on the observed data in the Implanted Population.

Another sensitivity analysis will be performed to assess the impact of missing data on the primary effectiveness analysis. Multiple imputation (van Buuren 2007) will be used for missing IOP data for patients lost to follow-up prior to Month 12 (see sample SAS code below). The worst observation carried forward (WOCF) method will be used to impute missing IOP data following non-study surgical procedures for IOP control or device explant and missing concomitant IOP-lowering medication counts.

```
proc mi data=eff out=mi seed=123456 nimpute=20;
  where eos='lost to follow-up';
  class sex race;
  fcs nbiter = 100 reg(/details);
  var iop12 iop10 iop08 iop06 iop03 iop01 iopb medcntb age sex race;
run;
```

The imputed IOP and/or medication counts will be used to derive the missing binary outcomes for the primary effectiveness analysis. The estimation of proportion and the standard error of the estimation will be calculated for each imputation based on primary analysis model:

```
proc genmod data=mi(where=(visit gt 0)) descending;
  by _imputation_;
  class visit pid;
  model resp=bliop visit/link=logit dist=bin;
  repeated subject=pid/type=un within=visit;
  lsmeans visit/cl alpha=0.05;
  ods output lsmeans=lsms(keep=visit estimate lower upper);
run;
```

PROC MIANALYZE procedure available in SAS software will be used to combine results and generate the overall estimate and corresponding 2-sided 95% CI; see sample SAS code below:

```
proc mianalyze data=lsms;
  modeffects prop;
  stderr prop_se;
  ods output parameterestimates=miresult;
run;
```

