### **14.0 DETERMINATION OF SAMPLE SIZE**

Fifty patients will provide a precision of at least  $\pm 0.145$  to estimate the proportion of patients achieving an IOP reduction  $\geq 20\%$  at 12 months on the same number or fewer IOP-lowering medications compared with baseline based on a 95% exact Clopper-Pearson CI for binomial proportions. Sixty-five patients will be implanted to ensure at least 50 evaluable patients who are defined as implanted patients with 12 months of follow-up.

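### SAP 10.1.2: the sample PROC MI code fits the imputation model only on patients lost to follow-up, so Month 12 IOP cannot be imputed as shown

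*SAP*

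**What the plan says.** SAP 10.1.2 plans two sensitivity analyses for the primary endpoint. One describes the observed data. The other addresses missing data by two rules. Multiple imputation "will be used for missing IOP data for patients lost to follow-up prior to Month 12". Worst observation carried forward (WOCF) covers IOP missing after non-study IOP surgery or explant, and missing medication counts.

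The imputation is set out in sample SAS code. PROC MI reads `eff`, writes `mi` with 20 imputations, and uses fully conditional specification with linear regression. The variables are `iop12`, the five earlier post-baseline IOP values, baseline IOP, baseline medication count, age, sex and race. The same step carries the statement "where eos='lost to follow-up". PROC GENMOD then reads `mi` by imputation, and PROC MIANALYZE pools the results.

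Two other places matter. SAP 10.1.1 says of the primary model: "In fitting the above model, missing data will not be imputed". SAP 16.1 assigns assessments to visits by study day, and Month 12 is Day 336 or later.

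**The concern.** The prose uses loss to follow-up to say whose IOP is to be filled in. The code uses it to choose the rows that PROC MI reads. These are different jobs. A regression for Month 12 IOP must be estimated on patients who have a Month 12 IOP before it can be applied to patients who do not. The filter keeps the second group and drops the first.

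The primary model imputes nothing and the other sensitivity analysis uses observed data. This is therefore the only planned analysis that imputes for the primary endpoint. If its imputation step has no Month 12 data to learn from, it cannot show how far the lost patients might move the result.

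**Working it through.** **1. The plan's own figure.** SAP 14.0 gives a precision of ±0.145 with 50 patients. The exact 95% Clopper-Pearson interval for 25/50 is 0.3553 to 0.6447, and (0.6447 − 0.3553)/2 = 0.1447. The figure reproduces and is not in dispute; it serves here only for scale.

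**2. Rows PROC MI reads.** SAP 14.0: "Sixty-five patients will be implanted to ensure at least 50 evaluable patients who are defined as implanted patients with 12 months of follow-up". If that target is met, at most 65 − 50 = 15 patients are non-evaluable. All reasons for leaving share those 15, so the number lost to follow-up, k, lies between 0 and 15. The documents give no expected value.

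**3. Observed `iop12` among those rows.** A patient lost before Month 12 has no Month 12 IOP, so the count is 0 whatever k is and whenever patients leave. There are two narrow exceptions: an efficacy assessment on Day 336 or later in a patient still coded as lost, or a WOCF value written into `iop12` before PROC MI runs. An exit assessment before Day 336 falls in an earlier window and does not help.

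**4. Could a few exceptional values suffice?** The regression of `iop12` on the other ten variables has an intercept (1), eight continuous predictors (8), sex (1) and race. Race contributes 1 coefficient with the two levels of SAP 10.1.3 and 5 with the six levels of SAP 8.1.

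- Coefficients: 1 + 8 + 1 + 1 = 11, up to 1 + 8 + 1 + 5 = 15.
- Observed `iop12` values needed for one residual degree of freedom: 12 to 16.

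These would have to come from at most 15 patients who have essentially none.

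**5. With and without the filter.**

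| | Filter as shown | Filter removed |
|---|---|---|
| Patients read | k (0 to 15 if at least 50 complete) | 65 |
| Source of observed `iop12` | none, apart from the exceptions in step 3 | completers with a usable Month 12 IOP |

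Fifty completers need not mean 50 usable values. SAP 10.0 excludes IOP after non-study IOP surgery, and Protocol 6.5 does not list such surgery without explant as a mandatory withdrawal.

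**6. The next step.** The output `mi` holds only the rows PROC MI read. No step shown adds the completers before PROC GENMOD reads it, so as printed the model would describe the lost subset and not the Implanted Population.

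**7. Size.** If the outcomes of k lost patients are open, the crude proportion can differ by k/65 between none and all of them responding.

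| k | k/65 |
|---|---|
| 0 | 0 |
| 5 | 0.077 |
| 10 | 0.154 |
| 15 | 0.231 |

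The row for 15 is a ceiling, because it assigns the whole non-evaluable allowance to loss to follow-up. These are crude proportions, not model estimates. SAS was not run, so I make no claim about whether the step would stop with an error or return unfilled values.

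**The case against.** The strongest reply is that the block is labelled as sample code and is plainly incomplete. PROC MI works on one row per patient, while GENMOD needs one row per visit with the derived response, and no restructuring is shown. The prose says who is imputed, cites a methods paper on fully conditional specification, and says that a proportion and its standard error are calculated for each imputation. Run word for word, the chain would lack variables it needs, so it is unlikely to yield a wrong result unnoticed. Nothing is tested formally and no decision rests on this analysis.

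Much of that stands, and it limits the weight of the point. It does not remove it. The variable list and the fitting set appear only in the code, and no sentence says that completers inform the model. The amendment log records a clarification of this code, so it is meant to be followed. Merging completers back later would repair the GENMOD input but not a model already fitted without them.

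The prior trial in Protocol 2.1 gives a hint of scale: 65 patients at baseline, 52 with Month 12 medication data, and 13.8% (about 9) with secondary surgery. If those 9 are among the 65 − 52 = 13 without data, 4 remain and 4/65 = 0.062. If none are, 13/65 = 0.20. Reasons for missing data are not given there and the population differs, so this is no estimate of k.

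Some stronger readings are tempting but unsupported:

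- A reader might take the prior trial's rate ("At Month 12, 76% of subjects achieved" the response), set 0.76 × 50 = 38 responders, and infer that the defect leaves the result anywhere from 38/65 = 0.585 to 53/65 = 0.815. That treats all 15 non-evaluable patients as lost and borrows a response rate. It describes missing data in general, not the effect of this line.
- A reader might infer that pooling on the proportion scale is wrong. Nothing in the documents shows an error in that choice.
- A reader might infer a proven gap for other departures. SAP 7.0 lists further reasons for leaving, and under Protocol 6.5 patients who "have a suture placed to close the scleral channel, will be withdrawn from the study". Neither imputation rule names scleral-suture withdrawals. Whether the SAP's planned look-up table of non-study IOP procedures will cover a suture cannot be told from the documents. This is a separate clarification.

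**Conclusion.** The point holds for the code as shown. The WHERE statement restricts the imputation model to patients who by definition lack the value being modelled, so the Month 12 regression cannot be estimated. That rests on the SAP's own description of the patients and its Day 336 window, not on any assumed dropout pattern.

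The reach is narrow: the multiple-imputation part of one sensitivity analysis. The primary analysis, the observed-data analysis, the WOCF rule (specified in prose) and the sample size stand. A reader might infer that the primary estimate is compromised; it is not, because that model does not impute. The consequence is k/65 of the crude proportion left uninformed by the imputation, with k unknown and no effect if k = 0. It should be corrected before the analysis is programmed, because the change is trivial and no other planned analysis imputes for the primary endpoint.

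**What to change.** In the SAP 10.1.2 code:

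1. Delete the WHERE statement and fit PROC MI on the full Implanted Population.
2. PROC MI will then fill every missing IOP it meets. Keep the imputed IOP only for the patients the SAP designates for multiple imputation, and set the others back to missing.
3. Apply WOCF to IOP after non-study IOP surgery or explant, replacing any value PROC MI put there, and to missing medication counts as already planned.
4. Derive the response and fit GENMOD by `_imputation_` on the full Implanted Population.
5. While the code is open, carry `_imputation_`, visit, and an estimate with its standard error through to PROC MIANALYZE. The current KEEP list omits the first and last of these, and `prop` and `prop_se` are not created in the code shown. Pool by visit on whichever scale the sponsor chooses, with Month 12 for the primary endpoint.

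As a separate clarification, one sentence could say how IOP missing for reasons outside both rules is handled. Whether multiple imputation extends to those patients is the sponsor's choice of estimand.

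Cost: one deleted line, a few added lines of sample code and a sentence of SAP wording. No new data are needed, and the primary analysis does not change.

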## **10.1 PRIMARY EFFECTIVENESS ASSESSMENTS**

### **10.1.1 Primary Analysis**

The primary effectiveness analysis will estimate the proportion of patients, with corresponding 2-sided 95% CI, that achieve at least a 20% reduction from baseline Hour 0 IOP while on the same number or fewer IOP-lowering medications at Month 12 compared with baseline using a mixed-effects repeated measures logistic regression model. The model will include visit as a fixed effect and baseline IOP as a covariate for repeated measures at Month 1, 3, 6, 8, 10, and 12. An unstructured covariance matrix will be used for repeated measures on the same patient; if the model with unstructured covariance fails to converge, an alternative covariance structure will be chosen. The Hour 0 IOP percent change from baseline at a timepoint is calculated as:

$$100 \times (\text{Timepoint Hour 0 IOP} - \text{Baseline Hour 0 IOP}) / \text{Baseline Hour 0 IOP}$$

First, a response variable will be derived from the effectiveness variables: Hour 0 IOP percent change from baseline and the number of concomitant IOP-lowering medications. If the percent change in Hour 0 IOP from baseline is less than or equal to  $-20\%$  at an analysis timepoint of interest **and** the number of IOP-lowering medications taken at the that timepoint is same or fewer compared to that at baseline, the response variable will be coded to value 1 and 0 otherwise. Refer to Section 8.4.2 for a discussion on determining the number of IOP-lowering medications taken at a timepoint of interest. GENMOD procedure available in SAS software will be used to fit the repeated measures logistic regression model; see sample SAS code below:

```
proc genmod data=one(where=(visit gt 0)) descending;
  class visit pid;
  model resp=bliop visit/link=logit dist=bin;
  repeated subject=pid/type=un within=visit;
  lsmeans visit/cl alpha=0.05;
  ods output lsmeans=lsms(keep=visit estimate lower upper);
run;
```

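### SAP 10.1.2: the printed multiple-imputation pooling step names variables its input lacks and is not split by visit, so it cannot return the Month 12 responder rate

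*SAP*

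**What the plan says.** SAP 10.1.1 defines the target as the proportion of patients with at least a 20% fall in Hour 0 IOP "while on the same number or fewer IOP-lowering medications at Month 12 compared with baseline". The model has visit as a fixed effect and "baseline IOP as a covariate for repeated measures at Month 1, 3, 6, 8, 10, and 12". It therefore yields six visit-specific LS means on the logit scale, and 10.1.1 explains how to back-transform each estimate and its limits.

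SAP 10.1.2 then tests this result against missing data. The printed sequence is:

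- Imputation: "proc mi data=eff out=mi seed=123456 nimpute=20", that is, 20 completed datasets.
- Model fit: the GENMOD model of 10.1.1, run "by _imputation"`_`, with LS means saved by "ods output lsmeans=lsms(keep=visit estimate lower upper"`)`.
- Pooling: PROC MIANALYZE reads `lsms` directly, with "modeffects prop" and `prop_se` as the standard error. It has no BY statement and no restriction to Month 12.

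The prose says that a proportion and its standard error will be calculated for each imputation. It gives no formula for either, no pooling scale and no visit. The stated purpose of the last step is that "PROC MIANALYZE procedure available in SAS software will be used to combine results and generate the overall estimate and corresponding 2-sided 95% CI".

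**The concern.** The printed step has two separate faults.

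1. **Missing inputs.** `prop` and `prop_se` are not among the four variables kept in `lsms`. The standard error of the LS mean, from which `prop_se` would normally be built, is dropped by the same keep list, and so is the imputation index.
2. **No split by visit.** Even with the two variables supplied, the pooling step does not know that its rows belong to six different visits.

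The first fault shows itself, because the program stops. The second does not: once the variables exist, the step runs without complaint and prints one plausible proportion with a 95% CI.

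The other sensitivity analysis in 10.1.2 is a descriptive summary of observed data. This is therefore the only visible analysis that asks what imputing the missing outcomes does to the primary result. The plan implants 65 patients to secure 50 with 12 months of follow-up, which allows for up to 15/65 = 23% without it, so the question is not idle.

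**Working it through.** **The plan's own figure.** The SAP gives no number for the pooling step. The nearest yardstick is the precision in SAP 14.0, ±0.145 for 50 patients. The exact Clopper-Pearson interval at 25/50 is 0.3553 to 0.6447, a half-width of 0.1447, so that figure reproduces. It is used here only for scale.

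**Step 1: compare the columns.**

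| Needed by the pooling step | Kept in `lsms`? |
|---|---|
| `prop` | no |
| `prop_se` | no |
| a visit split | `visit` is kept but not used |

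The step as printed has no effect and no standard error to read.

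**Step 2: count the rows.** 6 visits x 20 imputations = 120 rows. A Month 12 result should rest on 20 of them. Without BY visit, all 120 are read as 120 imputations of a single quantity.

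**Step 3: apply Rubin's rules both ways.** With m rows, q̄ is the mean of the row estimates, W the mean within-row variance and B the variance between rows. The total variance is T = W + (1 + 1/m)B, and SE = √T.

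Assumptions, none of them from the documents: responder rates by visit as listed, within-imputation variance p(1 − p)/65, and simulated between-imputation scatter with SD 0.02. The scatter was re-centred so that each visit's mean equals its assumed rate.

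Worked case, with rates 0.90, 0.85, 0.78, 0.74, 0.70 and 0.65 at Months 1, 3, 6, 8, 10 and 12:

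- Month 12 only (m = 20): q̄ = 0.650, W = 0.003495, B = 0.000334. T = 0.003495 + 1.05 x 0.000334 = 0.003846, so SE = 0.062.
- All rows (m = 120): q̄ = 4.62/6 = 0.770, W = 0.002608, B = 0.007611. T = 0.002608 + (1 + 1/120) x 0.007611 = 0.010283, so SE = 0.101.

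B is about 23 times larger in the second line (0.007611/0.000334). Nearly all of it is the spread between visits: squared deviations of the six rates from 0.77 sum to 0.0436, and 20 x 0.0436/119 = 0.0073.

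| Assumed rates, Months 1, 3, 6, 8, 10, 12 | Month 12 pooled (95% CI) | All 120 rows pooled (95% CI) | Difference |
|---|---|---|---|
| 0.90, 0.85, 0.78, 0.74, 0.70, 0.65 | 0.650 (0.528–0.772) | 0.770 (0.570–0.970) | +0.120 |
| 0.85, 0.83, 0.81, 0.79, 0.78, 0.76 | 0.760 (0.649–0.871) | 0.803 (0.684–0.923) | +0.043 |
| 0.76 at every visit | 0.760 (0.653–0.867) | 0.760 (0.651–0.869) | 0 |
| 0.55, 0.60, 0.66, 0.70, 0.73, 0.76 | 0.760 (0.648–0.872) | 0.667 (0.480–0.854) | −0.093 |

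The difference is simply the all-visit mean minus the Month 12 rate, so its sign follows the direction of change over time. The largest shift shown, 12.0 points, approaches the ±14.5 points that the trial is sized for.

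**Step 4: can the inputs be recovered?** Yes. On the logit scale SE = (upper − lower)/(2 x 1.96), and the delta method gives a proportion-scale SE of p(1 − p) x SE(logit). For p = 0.76 and 65 patients, SE(logit) = 1/√(65 x 0.1824) = 0.290, and the proportion-scale SE is 0.1824 x 0.290 = 0.053. The SAP does not say which route to take.

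**The case against.** The best defence is that the code is labelled as a sample and is schematic throughout. PROC MI works on one row per patient, while the next step reads one row per visit from a dataset of the same name. The carry-forward rule and the responder derivation have no code either. Unshown data steps are plainly assumed, and the prose does call for a proportion and its standard error per imputation. In a sentence about combining imputations, an overall estimate most naturally means pooled across imputations, not across visits. Section 10.1.1 tabulates results by visit, and the table specifications sit in a separate document. An experienced programmer may well do the right thing.

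Much of that stands, and it lowers the likely harm. It does not repair the step. This code is the only place where the pooling is specified, and neither it nor the surrounding prose names the visit or the scale.

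A reader might infer four stronger points, which the documents do not support:

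- That the code as printed returns a biased rate. It returns nothing. The biased figure needs a programmer who supplies the two variables and overlooks the visit column.
- That the result would be falsely reassuring because response fades after surgery. No responder rates before Month 12 are given; the background quotes only a Month 12 figure (76%) from the earlier 65-patient study. A rising profile errs the other way.
- That pooling proportions is itself a mistake. It is valid with a delta-method standard error, if the SAP says so.
- That the primary result is at risk. It does not use this step, and SAP 10.0 says that no formal hypothesis will be tested.

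**Conclusion.** The printed pooling step is wrong as written. It will not run, and if only `prop` and `prop_se` are added it estimates an all-visit average instead of the Month 12 rate, with an interval that treats change over time as imputation uncertainty. That misreading costs nothing if response is flat and 4.3, 9.3 and 12.0 points in the three changing profiles above, in either direction. These sizes rest wholly on the assumed visit rates, the 0.02 between-imputation SD and 65 patients per visit. The column mismatch and the missing visit split rest on no assumption. Severity is moderate to minor: a specification error confined to a sensitivity analysis, worth correcting before database lock so that the visit and the scale are not chosen afterwards.

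**What to change.** In SAP 10.1.2:

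1. Keep `_imputation_`, `visit`, `estimate` and `stderr` from the GENMOD LS means.
2. Sort by `visit` and `_imputation_`.
3. Run PROC MIANALYZE with BY visit (or restricted to Month 12), with `modeffects estimate; stderr stderr;`, so that pooling is on the logit scale.
4. Back-transform the pooled estimate and its limits by the inverse logit, as in 10.1.1. The logit scale is proposed for consistency with the primary analysis. If the proportion scale is preferred, state the delta-method standard error.
5. In the prose, describe the result as the Month 12 estimate pooled across imputations, with any other visits reported separately.

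The cost is a few lines of sample code and one phrase. Nothing changes in data collection, trial conduct or the primary analysis.
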